### 13.3 Interim Monitoring Plan

See section 6

### 13.4 Analysis of Primary Endpoints

See section 13.1

### 13.5 Analysis of Secondary Endpoints

See section 13.1

### 13.6 Reporting and Exclusions

Participants who never start protocol therapy will be excluded (“inevaluable”) from the analysis.

#### 13.6.1 Evaluation of Toxicity

All participants will be evaluable for toxicity from the time of their first treatment.

#### 13.6.2 Evaluation of the Primary Efficacy Endpoint

Analyses are intent-to-treat. Specifically, all eligible participants included in the study must be assessed for response/outcome to therapy, even if there are major protocol

therapy deviations.

Sub-analyses may then be performed on the basis of a subset of participants, excluding those for whom major protocol deviations have been identified (e.g., early death due to other reasons, early discontinuation of treatment, major protocol violations, etc.). However, these sub-analyses may not serve as the basis for drawing conclusions concerning treatment efficacy, and the reasons for excluding participants from the analysis should be clearly reported.

#### **14. PUBLICATION PLAN**

The results should be made public within 24 months of reaching the end of the study. The end of the study is the time point at which the last data items are to be reported, or after the outcome data are sufficiently mature for analysis, as defined in the section on Sample Size, Accrual Rate and Study Duration. If a report is planned to be published in a peer-reviewed journal, then that initial release may be an abstract that meets the requirements of the International Committee of Medical Journal Editors. A full report of the outcomes should be made public no later than three (3) years after the end of the study.

**Randomization process**

Within the Dana Farber/Harvard Cancer Center, randomized comparative studies are conducted in a manner such that for a blinded randomization, the individual assigning study treatment is not a member of the study team but from the office for the Office of Data Quality (ODQ). Central randomization is performed according to an algorithm provided by the statistician. This was in a permuted blocks algorithm, with block size of 4. Randomized treatment assignment was delivered to research pharmacy at the site in an unblinded fashion, and pharmacy dispense blinded study drug. ODQ has extensive experience working with both local and distant research pharmacies on blinded randomized placebo-controlled studies, and the system is already in place.

**Primary End-Point**

**Our primary endpoint will be the proportion of patients in each group that have a decrease of 10% or more in LVEF to <55% from baseline to 12 months after initiation of anthracyclines.**

*Assumptions for Sample Size Calculation:* We anticipated that 20% of the patients in the placebo group will reach the primary end-point. This assumption is based on significant prior literature; specifically, Limat *et al.* performed a prospective study where they enrolled patients similar to those proposed in this study (lymphoma receiving anthracycline-based chemotherapy) and performed a baseline measurement of LVEF and a measurement at 1 year. Their primary end-point was a more stringent cut-off than recommended by guidelines or being used in this study, a decrease of >15% in LVEF. They found that 20% of their population had a reduction of >15% in LVEF. Using CMR, two studies have tested the percentage of patients with a significant reduction in LVEF after anthracyclines. In a prospective observational study, Drafts and colleagues found that 26% of patients decreased their LVEF to <50% and in a prospective randomized study, Bosch and colleagues found that up to 33% of patients decreased their echocardiographically-derived LVEF to <55%. In the single small, randomized study which also used 40 mg of atorvastatin with 20 subjects in each arm, there was no decrease in LVEF after anthracyclines among patients on statins.

Our base case assumptions are as follows: 20% of the placebo group and 5% of the statin treatment group will meet the primary endpoint and we will be able to enroll 300 patients meeting all inclusion and exclusion criteria. From these, we anticipate a drop-out rate of approximately 10% due to a one-year mortality of  $\approx$ 5-6% and atorvastatin related side-effects

in 4-5% of patients. The remaining 270 patients will provide us with a > 90% power to detect a 15% difference in the proportions of those achieving the primary end-point at a two-sided significance level of 0.05. Moreover, we will have a 70% power if the difference in the percentage reaching the primary end-point between groups falls as low as 10%.

***Analysis Plan:*** The study is designed as a prospective double-blind randomized study. All statistical analyses will be performed based on intent-to-treat and repeat imaging will be performed at 1 year in all patients. In particular, we will include subjects who could not complete the study protocol due to statin toxicity and patients who started anthracyclines but did not complete the entire scheduled protocol. Chi-square analysis will be used to determine whether statins decrease the primary end-point.

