## 1.0 OBJECTIVES

The purpose of this protocol is to test the effect of statin therapy, as compared to placebo, on the cardiac dysfunction after administration of anthracyclines among patients with lymphoma.

Anthracyclines are a mainstay of cancer treatment with more than 100,000 patients treated per year with anthracyclines in the United States; however, their use is associated with increased rates of heart failure and left ventricular (LV) dysfunction. Once anthracycline-induced cardiotoxicity (AIC) is symptomatic, survival is dramatically decreased. There is significant scientific plausibility and supportive observational data that statins may protect the heart during the administration of anthracyclines. STOP-CA (Statins TO Prevent the Cardiotoxicity from Anthracyclines) is a multi-center randomized double-blind placebo controlled trial, in 270 statin-naive patients who will be randomized 1:1 to atorvastatin 40mg/daily or placebo to determine whether atorvastatin started prior to anthracyclines reduces anthracycline-induced cardiotoxicity (AIC) among patients with newly diagnosed lymphoma. The endpoint AIC is defined based on expert consensus as a  $\geq 10\%$  reduction in LVEF to  $< 55\%$  within the first 12 months after therapy. LVEF will be measured using the gold-standard, cardiac magnetic resonance (CMR), performed in an established core clinical trials laboratory by expert readers. Participants will be recruited over 3 years from large volume academic oncology networks. Myocardial fibrosis is a key intermediary that occurs prior to the development of LV dysfunction. CMR is the gold-standard imaging technique for fibrosis; therefore, to test whether the sub-acute development of myocardial fibrosis can predict the late occurrence of AIC and whether statins reduce myocardial fibrosis, we also propose measuring the extent of fibrosis at baseline and 6 months. We hypothesize that statins will attenuate myocardial fibrosis and that the extent of early fibrosis will predict the decrease in LVEF at 12 months. Both echocardiography and serum troponin are more widely available than CMR; therefore, in a third aim, we will test whether strain by echocardiography and troponin levels measured early during chemotherapy (after 4 of 8 standard cycles,  $\approx 3$  months), can identify patients at high risk of AIC.

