#### **Primary End-Point**

**Our primary endpoint will be the proportion of patients in each group that have a decrease of 10% or more in LVEF to <55% from baseline to 12 months after initiation of anthracyclines.**

**Assumptions:** We anticipate that 20% of the patients in the placebo group will reach the primary end-point. This assumption is based on significant prior literature; specifically, Limat *et al.* performed a prospective study where they enrolled patients similar to those proposed in this study (lymphoma receiving anthracycline-based chemotherapy) and performed a baseline measurement of LVEF and a measurement at 1 year. Their primary end-point was a more stringent cut-off than recommended by guidelines or being used in this study, a decrease of >15% in LVEF. They found that 20% of their population had a reduction of >15% in LVEF. Using CMR, two studies have tested the percentage of patients with a significant reduction in LVEF after anthracyclines. In a prospective observational study, Drafts and colleagues found

that 26% of patients decreased their LVEF to <50% and in a prospective randomized study, Bosch and colleagues found that up to 33% of patients decreased their LVEF to <55%. In the single small randomized study which also used 40 mg of atorvastatin with 20 subjects in each arm, there was no decrease in LVEF after anthracyclines among patients on statins. Our base case assumptions are as follows: 20% of the placebo group and 5% of the statin treatment group will meet the primary endpoint and we will be able to enroll 300 patients meeting all inclusion and exclusion criteria. From these, we anticipate a drop-out rate of approximately 10% due to a one year mortality of  $\approx$ 5% and atorvastatin related side-effects in 4% of patients. The remaining 270 patients will provide us with a 98% power to detect a 15% difference in the proportions of those achieving the primary end-point at a one-sided significance level of 0.05. Moreover, we will have a 70% power if the difference in the percentage reaching the primary end-point between groups falls as low as 10%.

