### 13.2 Sample Size, Accrual Rate and Study Duration

**Feasibility:** In 2012, there were 412 patients with lymphoma treated with anthracyclines at MGH, DFCI and BWH (110 at MGH and 312 at DFCI and BWH). In the large cohort of lymphoma patients that we reported in our preliminary data, only 8% of patients ( $n=33$ ) were on statins at the time of chemotherapy and would be excluded. Even using the new more expansive cholesterol guidelines and assuming that all the patients who were eligible to receive statins were treated with statins, more than 80% of patients ( $n=330$ ) would be eligible for enrollment annually. In aggregate, less than 30 of the remaining 330 patients would be excluded based on these criteria and this would leave a final total of 300 patients with lymphoma per year that would meet entry criteria and not meet exclusion criteria. Based on prior trials recruited by this group, we anticipate enrollment of 33% of eligible patients ( $\approx 100$  per year, 8 per month); 5-6 patients per month will be enrolled from DFCI/BWH and 2-3 patients per month from the MGH. We expect a total of about 3 years to complete enrollment.

In total 300 patients need to be enrolled.

Accrual Targets
------------------------

Ethnic Category	Sex/Gender			
	Females		Males	Total
Hispanic or Latino	25	+	26	= 51
Not Hispanic or Latino	125	+	124	= 249
Ethnic Category: Total of all subjects	150 (A1)	+	150	= 300
Racial Category				
American Indian or Alaskan Native	0	+	0	= 0
Asian	16	+	15	= 31
Black or African American	14	+	13	= 27
Native Hawaiian or other Pacific Islander	0	+	0	= 0
White	115	+	117	= 232
Racial Category: Total of all subjects	150(A2)	+	150 (B2)	= 300 (C2)

(A1 = A2)

(B1 = B2)

(C1 = C2)

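### The SAP moves to two-sided 0.05 but keeps the protocol's 70% power for a 10-point difference; 270 patients give about 64%

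*SAP*

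**What the plan says.** Protocol 13.1, Primary End-Point, assumes 20% of placebo and 5% of statin patients reach the endpoint. It expects 300 enrolled and 270 left after about 10% drop-out, and claims a "98% power to detect a 15% difference in the proportions of those achieving the primary end-point at a one-sided significance level of 0.05". It then gives 70% power for a 10-point difference.

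The SAP's Primary End-Point section keeps the same rates and the same 270 patients but changes the level: "The remaining 270 patients will provide us with a > 90% power to detect a 15% difference in the proportions", this time "at a two-sided significance level of 0.05". The next sentence is the protocol's, unchanged: "we will have a 70% power if the difference in the percentage reaching the primary end-point between groups falls as low as 10" percent.

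The analysis plan is the same in both documents: "Chi-square analysis will be used to determine whether statins decrease the primary end-point". It gives no level, no sidedness and no statement on continuity correction. For the primary endpoint, the level appears only in the two power paragraphs, and they disagree. (The levels given under Aims 2a and 3a concern other endpoints.)

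**The concern.** With sample size and event rates fixed, moving from one-sided 0.05 to two-sided 0.05 must lower power against a benefit. The SAP lowered the first of the two power figures and not the second, so the same 70% cannot be right for both levels under one test and one set of rates.

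The 70% is the only power figure the plan gives for a primary-endpoint effect smaller than 20% versus 5%. The 5% statin rate leans on a randomized study with 20 patients per arm, so a smaller effect is a realistic case. A reader of the SAP would put the chance of missing a true 10-point benefit at 30%.

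**Working it through.** **Inputs.** 270 analysed patients (SAP, Primary End-Point), allocated 1:1 (Protocol 1.0), so n = 135 per arm. Placebo rate 20% (both documents). The 10-point case is read as 20% versus 10%; the 10% is inferred, because 20% is the only placebo rate the plan assumes. Level 0.05, one-sided in the protocol and two-sided in the SAP.

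**Formula (normal approximation, uncorrected chi-square).** With d = p1 − p2 and p̄ = (p1 + p2)/2:

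- SE0 = √[2p̄(1 − p̄)/n]
- SE1 = √{[p1(1 − p1) + p2(1 − p2)]/n}
- power = Φ[(d − z·SE0)/SE1], with z = 1.645 one-sided or 1.960 two-sided

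The continuity correction replaces d by d − 1/n. Exact values sum the two binomial distributions over all tables that the test rejects.

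**Step 1: base case, 20% versus 5%.** SE0 = √(0.21875/135) = 0.04025; SE1 = √(0.2075/135) = 0.03920.

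- One-sided: (0.15 − 1.645 × 0.04025)/0.03920 = 2.137, power 98.4%. The protocol's 98% reproduces.
- Two-sided: (0.15 − 1.960 × 0.04025)/0.03920 = 1.814, power 96.5%. The SAP's claim of more than 90% is correct.

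**Step 2: 10-point case, 20% versus 10%.** SE0 = √(0.255/135) = 0.04346; SE1 = √(0.25/135) = 0.04303.

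- One-sided: (0.10 − 1.645 × 0.04346)/0.04303 = 0.663, power 74.6%.
- Two-sided: (0.10 − 1.960 × 0.04346)/0.04303 = 0.344, power 63.5%.
- Two-sided, continuity-corrected: d − 1/n = 0.0926; (0.0926 − 0.0852)/0.04303 = 0.172, power 56.8%.

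**Step 3: all versions of the test, 135 per arm.**

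| Test | 20% v 5%, one-sided | 20% v 10%, one-sided | 20% v 5%, two-sided | 20% v 10%, two-sided |
|---|---|---|---|---|
| Uncorrected, approximation | 98.4% | 74.6% | 96.5% | 63.5% |
| Uncorrected, exact enumeration | 98.9% | 75.5% | 97.5% | 64.1% |
| Continuity-corrected, approximation | 97.4% | 68.8% | 94.8% | 56.8% |
| Yates, exact enumeration | 98.1% | 69.7% | 96.2% | 57.5% |
| Fisher | 98.1% | 69.7% | 96.2% | 58.1% |

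One-sided Yates or Fisher power gives 98.1% and 69.7%, so a single method reproduces both protocol figures. This supports 20% versus 10% as the intended case and marks the SAP's 70% as a one-sided figure carried over. No two-sided version reaches 70%.

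**Step 4: size needed for 70%.** At two-sided 0.05, uncorrected, n = [1.960 × √0.255 + 0.524 × √0.25]²/0.10² = 1.2519²/0.01 = 156.7. That is 157 per arm, or 314 analysed, against 270 planned. With continuity correction it is 177 per arm (354).

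**The case against.** **The arm rates are inferred.** The 70% sentence gives only a difference. If the gap narrowed because the placebo rate was lower, 70% could be about right or low at the two-sided level: 17% versus 7% gives 71.7% uncorrected, and 15% versus 5% gives 72 to 81% depending on the test. The point is fair, but the plan assumes no placebo rate other than 20% and argues for that rate at length. Nor does 15% versus 5% explain where the 70% came from, since it gives 82 to 89% at the protocol's one-sided level. The higher rates quoted from the literature cut the other way: with 26% or 33% on placebo, a 10-point difference has about 52% or 45% power (uncorrected).

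**The 57 to 58% belongs to tests the plan does not name.** The SAP names chi-square for the primary endpoint and Fisher only for Aim 1b. This stands in part: under a plain chi-square the gap is about 6 points. The lower figure matters only because the plan does not say whether the chi-square is corrected, and because the protocol's 70% itself matches a corrected or exact test.

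**More than 270 may be analysed.** The intent-to-treat rule keeps patients who stop for statin toxicity. If only the 5 to 6% mortality were lost, 141 to 142 per arm would give 65 to 66% power; all 300 would give 68.1% uncorrected. Neither reaches 70%, and the SAP ties its power to the remaining 270.

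**It is a secondary figure.** This is true. A non-significant result is also better read from the estimate and its confidence interval than from design-stage power. That limits the consequence but does not make the number right.

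**Conclusion.** The concern holds. At the SAP's own level and sample size, power for 20% versus 10% is about 64% with an uncorrected chi-square test and 57 to 58% with a continuity-corrected or exact one. The chance of missing a true 10-point benefit is therefore about 36%, or 42 to 43%, rather than 30%. This rests on 135 analysed per arm and on the 20% placebo rate holding, so that the statin rate is 10%.

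At the protocol's one-sided level its own figures are sound: 98% is right, and 70% is right for a corrected or exact test and conservative for an uncorrected one. The error lies in repeating the 70% after the level changed. The base-case power, the sample size and the conduct of the trial are untouched.

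**What to change.** - **SAP, Primary End-Point:** replace the 70% with about 64%, stating the basis (uncorrected chi-square, two-sided 0.05, 20% versus 10%, 135 per arm). If a continuity-corrected or exact test will be used, give 57 to 58% instead.
- **Analysis plans in the SAP and Protocol 13.1:** state two-sided 0.05 and whether the chi-square test is continuity-corrected.
- **Protocol 13.1, power paragraph:** to agree with the SAP, change one-sided to two-sided, 98% to about 96%, and the 70% to the same corrected figure. This is alignment; the protocol's numbers are not wrong at its own level.
- **Minor wording:** Protocol 1.0 describes the trial as "in 270 statin-naive patients who will be randomized 1:1", while Protocol 13.2 says "In total 300 patients need to be enrolled". Make 1.0 read as 300 enrolled with 270 expected to remain.

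The cost is wording only. One secondary power figure becomes less favourable.

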## 10. STUDY CALENDAR

After consent is obtained, patients will undergo a baseline visit including a questionnaire, vital sign measurements, an MRI, echocardiogram and blood sampling. A pregnancy test (urine beta-HCG) will be performed as appropriate. A second visit similar to the first one will be scheduled after 3 cycles of chemotherapy (approx 3 months). The final study visit will be at 12 months where subjects will undergo an echo, MRI and blood sampling.

An additional visit for the sub-group in the MRI mechanistic sub-study will occur at 6 months where this sub-group will undergo an additional cardiac MRI.

We will do a balanced randomization with blocks of 2 patients for each cancer site.

Baseline evaluations are to be conducted within 1 week prior to start of anthracyclines therapy. Assessments must be performed prior to administration of any study agent. Study assessments and agents should be administered within  $\pm 7$  days of the protocol-specified date, unless otherwise noted.

	Pre-Study	Study Drug	1 month	2 months	3 months	6 months	12 months	24 months
Atorvastatin/placebo		X-----X						
Informed consent	X							
Demographics	X							
Medical history	X							
Perceived Stress Scale	X				X	X	X	
Physical exam	X				X		X	
Vital signs	X		X		X		X	

Height	X							
Weight	X					X	X	
Phone call: Adverse and clinical events	X		X	X	X	X	X	X
LFTS	X		X		X			
Lipids/Blood biomarkers	X				X		X	
B-HCG	X					X	X	
Echocardiogram	X				X		X	
MRI	X					X	X	
Pill count (Monthly)								

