### **Secondary End-Points Aim 1:**

**Aim 1a.** We will test whether cardiac risks factors (blood pressure, age, sex, glucose or cholesterol levels, prior history of cardiac disease, LVEF at baseline) or cancer specific risk factors (anthracycline dose, radiotherapy) are predictive of the effect of statins on LVEF.

***Analysis Plan:*** In patients treated with statins, we will use a logistic regression model to evaluate whether cardiac risks factors or cancer specific risk factors are predictive of the effect of statins on LVEF. Patients on statins and eligible for statins will be excluded. Therefore, cholesterol levels will be relatively homogenous, and we will not pre-stratify our cohort based on cholesterol. Radiotherapy is not routinely used in the cohort and is used in <5% of cases, there we will also not pre-stratify based on the use of radiotherapy. However, we will use cholesterol values (as a continuous variable) and the use of radiotherapy (as a binary variable) to perform a post-hoc analysis. Additionally, all patients are intended to have the same dose of anthracyclines and dose adjustments are made during therapy in response primarily to toxicities. Therefore, we will additionally test the interaction between the dose of anthracyclines and the effect of statins as a post-hoc analysis.

**Aim 1b.** We will test whether statins reduce cardiac events. The study is not powered to test the effect of atorvastatin on clinical events.

***Adjudication plan:*** The occurrence of clinical adverse cardiac events will be adjudicated based on consensus opinion of a clinical adjudication committee containing three board-certified cardiologists blinded to experimental group (Drs. [name], [name] and [name]).

***Analysis Plan:*** All statistical analyses will be performed based on intent-to-treat. Fisher exact tests will be used to determine whether statins decrease the combined end-point of death or heart failure.

**Aim 1c.** We will test whether statins are safe.

***Analysis Plan:*** Chi-square will be used to test for differences between the two treatment groups for categorical secondary endpoints.

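### The primary chi-square is valid but does not use baseline CMR LVEF; pre-specifying adjustment would add a little power with no new data

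*SAP*

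**What the plan says.** The SAP (Primary End-Point, Analysis Plan) states: "Chi-square analysis will be used to determine whether statins decrease the primary end-point". Protocol 13.1 says the same. No covariate, stratification term, effect measure or interval is given for the primary comparison.

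The endpoint is a fall in LVEF of 10 or more to below 55%, from baseline to 12 months. Protocol 1.2 makes clear that these are percentage points. Protocol Section 10 puts an MRI at the baseline visit for all patients.

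Baseline LVEF is used as a covariate only in Aim 1a, whose list of candidate predictors includes "prior history of cardiac disease, LVEF at baseline". That model is fitted in statin-treated patients only.

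On power, the SAP assumes that "20% of the placebo group and 5% of the statin treatment group will meet the primary endpoint", and continues: "The remaining 270 patients will provide us with a > 90% power to detect a 15% difference", "at a two-sided significance level of 0.05". For a smaller effect, "we will have a 70% power if the difference in the percentage reaching the primary end-point between groups falls as low as 10" percentage points. The protocol's own power statement is made "at a one-sided significance level of 0.05".

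On allocation, Protocol Section 10 says: "We will do a balanced randomization with blocks of 2 patients for each cancer site". Protocol 13.1 and the SAP (Randomization process) instead describe permuted blocks of 4 and name no stratification factor.

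**The concern.** Baseline LVEF is built into the outcome: whether a patient can fall by 10 points and also finish below 55% depends on where that patient starts. Every patient whose change can be computed has the baseline value. An analysis that leaves it out gives up some precision.

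Little is at stake at the design effect, where power is ample. It matters more near a 10-point difference, where power is modest. A second gap is that a test alone gives no estimate of how large the benefit is or how precisely it is known.

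**Working it through.** **1. The plan's own power.** With n = 135 per arm and pooled-variance normal approximation:

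power = Φ{ [ |p1 − p2| − z·√(2·p̄(1−p̄)/n) ] / √( [p1(1−p1) + p2(1−p2)]/n ) }

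- 20% v 5%, two-sided 0.05: p̄ = 0.125. (0.15 − 1.96 × 0.04025)/0.03921 = 1.814, so power is 96.5% (exact enumeration 97.5%). The SAP's figure of above 90% reproduces.
- 20% v 5%, one-sided 0.05: 98.4%. The protocol's 98% reproduces.
- 20% v 10%, two-sided: p̄ = 0.15. (0.10 − 1.96 × 0.04346)/0.04303 = 0.344, so power is 63.5% (exact 64.1%). The SAP does not say which two rates lie behind its 70%. If 20% v 10% is meant, 70% does not reproduce with 270 patients at two-sided 0.05; one-sided gives 74.6%.

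**2. Inputs for the gain from adjustment.**

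- Baseline LVEF 64±5, and 12-month SD 6 (no statin) or 9 (statin): Protocol 2.1 b, from 72 breast cancer patients.
- Correlation of baseline with 12-month LVEF: not given. Assumed range 0 to 0.85.
- Event: fall of at least 10 points and 12-month value below 55. The 12-month means were set so that event rates were 20% v 10% or 20% v 5%.

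**3. Like-for-like comparison.** 135 per arm, two-sided 0.05, 3,000 simulated trials per scenario. The unadjusted logistic score test (which is the chi-square) is set against the score test for arm after linear and quadratic baseline LVEF. Power in %:

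| 12-month SD | Correlation | Placebo risk by baseline fifth, low to high (%) | 20% v 10% | Gain | 20% v 5% | Gain |
|---|---|---|---|---|---|---|
| 6 | 0 | 4/13/24/29/29 | 66.0 → 67.9 | 1.9 | 96.7 → 97.5 | 0.8 |
| 6 | 0.3 | 9/18/27/27/19 | 62.3 → 63.7 | 1.4 | 97.5 → 97.7 | 0.2 |
| 6 | 0.5 | 14/22/28/24/12 | 64.5 → 66.2 | 1.7 | 97.2 → 97.4 | 0.2 |
| 6 | 0.7 | 20/25/28/20/6 | 62.6 → 64.2 | 1.6 | 97.4 → 97.5 | 0.1 |
| 6 | 0.85 | 29/28/28/14/1 | 62.8 → 65.6 | 2.8 | 97.5 → 97.4 | −0.1 |
| 9 | 0 | 7/15/23/27/27 | 64.3 → 65.9 | 1.6 | 97.2 → 97.3 | 0.1 |
| 9 | 0.3 | 15/21/25/24/16 | 64.8 → 65.6 | 0.8 | 97.6 → 97.9 | 0.3 |
| 9 | 0.5 | 22/24/25/20/9 | 66.6 → 67.4 | 0.8 | 97.5 → 97.4 | −0.1 |
| 9 | 0.7 | 32/26/23/13/3 | 64.3 → 66.0 | 1.7 | 97.9 → 98.4 | 0.5 |
| 9 | 0.85 | 46/28/19/7/1 | 63.8 → 70.4 | 6.6 | 97.7 → 98.7 | 1.0 |

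A second run with 4,000 trials per scenario gave gains at 20% v 10% of 0.9 to 1.2 points for correlations of 0.3 to 0.6, and 2.4 to 5 points at 0.8. At 20% v 5% it gave 0 to 0.9 points. Type I error stayed near 5%.

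**4. Analytic cross-check.** If baseline explains a share R² of outcome variance, effective n is about 135/(1 − R²). For correlations of 0.3 and 0.5 the simulated R² was 1.4% to 3.4%. At R² = 2%, n = 135/0.98 = 137.8, and power at 20% v 10% goes from 63.5% to 64.4%, worth about 6 patients in total. At R² = 5% it is 65.7%, worth about 14. This agrees with step 3.

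**5. Why a quadratic term.** At SD 6 and correlation 0.5, risk rises and then falls with baseline, and the linear R² is about 0. There a linear term alone adds 0.2 points (64.5 → 64.7) against 1.7 with the quadratic.

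**6. Events available.** At the design effect, 135 × 0.20 + 135 × 0.05 = 27 + 6.75, about 34.

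**The case against.** The case for leaving the plan alone is reasonable. A chi-square comparing two randomised proportions is valid, matches the endpoint as defined, and is the test on which the sample size rests. At the design effect, adjustment changes almost nothing. The gain at 20% v 10% is also near the limit of what simulation can resolve. The standard error of a paired power difference is about 0.5 to 0.6 points at 1,500 trials, hence about 0.31 to 0.37 at 4,000 (multiply by √(1,500/4,000) = 0.61). A gain of about 1 point is then roughly three standard errors from zero: real, but small. The inputs are borrowed or assumed. With about 34 events the model cannot carry many terms. All of this stands, and it limits the point to an optional improvement.

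A reader might infer three stronger things that the documents do not support:

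- **That chance imbalance in baseline LVEF distorts the primary result.** The test's type I error already allows for chance imbalance. Where risk is not monotone in baseline, a difference in mean baseline LVEF may barely move the result. The documents also do not establish baseline LVEF as prognostic; Aim 1a lists it as a factor still to be examined.
- **That the test is conservative because it ignores stratification by centre.** This would need allocation stratified by centre and centre to be prognostic. The only support is the Section 10 sentence, in which the site could be a centre or a disease site. It conflicts with the blocks of 4 and no named factor in Protocol 13.1 and the SAP.
- **That adjustment would restore the SAP's 70% power.** Under most assumptions it moves about 63.5% by 1 to 3 points. The 70% figure is a separate matter.

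**Conclusion.** The point holds as a minor, low-cost improvement. The planned test is sound, but it leaves unused a covariate that the endpoint itself requires.

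The gain is about 1 point of power at 20% v 10% with 135 per arm for correlations of 0.3 to 0.6. It rises to several points only at high correlations (0.8 and above), and at 20% v 5% it is close to nil. These figures rest on an assumed correlation, a baseline distribution from breast cancer patients, approximate normality, and 20% v 10% as the reading of a 10-point difference.

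A pre-specified risk difference with an interval is worth having even if the power gain is negligible. Nothing here shows bias or an inflated error rate in the current plan, and no claim about centre can be made until the randomisation text is settled.

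**What to change.** - **Reconcile the randomisation text first.** Protocol Section 10 (blocks of 2 by site) must agree with Protocol 13.1 and the SAP (blocks of 4, no factor named). State what was actually done and what site means.
- **Change the primary analysis in both documents, before unblinding.** Use logistic regression of the primary endpoint on arm, with baseline CMR LVEF as linear and quadratic terms. Name the test of the arm term and its sidedness, since the two documents currently differ on sidedness.
- **Report the standardised risk difference with a 95% CI.** Standardising over the trial population avoids presenting a conditional odds ratio as the treatment effect. State how the interval is obtained.
- **Keep the unadjusted chi-square as a supportive analysis.**
- **Add centre to the model, or use a Cochran-Mantel-Haenszel test by centre, only if** allocation was in fact stratified by centre and the strata are not sparse. The protocol allows external sites and does not give their number.

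The cost is a text change to the SAP and to Protocol 13.1, with no extra patients, visits or measurements. The downside is a slightly more complex model with about 34 events expected at the design effect. If treatment codes have already been opened, the adjusted analysis can only be supportive.
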